5.3 Dose Schema

5.3.1 Part A Interpatient dosing:

Part A is restricted to patients < 18 years of age. The starting dose will be 24 mg/m²/dose BID (Dose Level 1) with dose levels for subsequent groups of patients as follows.

Dose Level	Dose (mg/m ²)
-1	18 mg/m ² /dose BID (maximum 30 mg/dose BID)
1*	24 mg/m²/dose BID (maximum 40 mg/dose BID)

* Starting Dose Level

There will be no planned escalations beyond Dose Level 1 (24 mg/m²), the adult RP2D. Please see dosing nomogram in [Appendix V](#).

If the MTD has been exceeded at the first dose level, then the subsequent cohort of patients will be treated at a dose of 18 mg/m²/dose BID (Dose Level -1). If Dose Level -1 is not well tolerated, further de-escalation will not occur and Part A will close to accrual and Part B will continue and be limited to those age 18 years and older.

Note: Part A, PK expansion cohort will be opened when the RP2D/MTD has been defined and treated at that RP2D/MTD. If required number of responses per the Simon two-stage design for expansion is not met for either the ARMS or EWS phase 2 cohorts whilst the PK expansion is still enrolling, the PK expansion will be closed to those patients. Patients who have qualifying DDR alterations will always be allowed on the PK expansion cohort.

5.3.2 Part B Dose Level:

Patients <18 years of age in the B1, B2 and B3 phase 2 expansion cohorts defined in [section 4.1.2](#) will be treated at the RP2D/MTD defined in Part A. Patients ≥ 18 years of age will be treated at the adult RP2D (40 mg BID 3 days on and 4 days off of each week of a 28 day cycle).

If the patient experiences a toxicity, please refer to [Section 6.0](#) for dose modifications.

5.3.3 Intra-Patient Escalation:

Intra-patient dose escalation is not allowed.

5.4 Grading of Adverse Events

Adverse events (toxicities) will be graded according to the NCI Common Terminology Criteria for Adverse Events (CTCAE) version 5.0. All appropriate treatment areas should have access to a copy of the CTCAE version 5.0. A copy of the CTCAE version 5.0 can be downloaded from the CTEP website (http://ctep.cancer.gov/protocolDevelopment/electronic_applications/ctc.htm). Any suspected or confirmed dose-limiting toxicity should be reported immediately (within 24 hours) to the Study Chair. For laboratory values in CTCAE with grading definitions including both baseline and ULN definitions, utilize the ULN for CTCAE grading.

5.5 Definition of Dose-Limiting Toxicity (DLT)

DLT will be defined as any of the following events that are possibly, probably or definitely attributable to protocol therapy. The DLT observation period for the purposes of study dose-escalation (Part A) will be the first cycle of therapy. Please refer to [Section 13.5.4](#) for AE resolution definitions

Dose limiting hematological and non-hematological toxicities are defined differently.

5.5.1 Non-Hematological Dose-Limiting Toxicity:**5.5.1.1 Any Grade 3 or greater non-hematological toxicity attributable to protocol therapy with the specific exclusion of:**

- Grade 3 nausea and vomiting of < 3 days duration
- Grade 3 liver enzyme elevation, including ALT/AST/GGT that returns to Grade \leq 1 within 7 days. See [Appendix IV](#) for Adverse Event grading for liver function grading parameters in children and adolescents.

Note: For the purposes of this study the ULN for ALT is defined as 45 U/L.

- Grade 3 hypophosphatemia, hypokalemia, hypocalcemia or hypomagnesemia responsive to supplementation
- Any Grade 2 non-hematological toxicity that persists for \geq 7 days and is considered sufficiently medically significant or sufficiently intolerable by patients that it requires treatment interruption.
- Note: Allergic reactions that necessitate discontinuation of study drug will not be considered a dose-limiting toxicity.

5.5.2 Hematological dose limiting toxicity:

- Grade 4 neutropenia (ANC $< 500/\mu\text{L}$) that persists for \geq 7 days despite holding BAY 1895344 (elimusertib) for 3 days
- Grade 4 thrombocytopenia (Platelet count $< 25,000/\mu\text{L}$)
- Grade 3 thrombocytopenia (Platelet count $< 50,000/\mu\text{L}$) that persists for \geq 7 days despite holding BAY 1895344 (elimusertib) for 3 days *OR* is associated with clinically significant bleeding
- Failure to meet hematological criteria to initiate weekly dosing ([Section 5.2.1](#)) or subsequent cycles of therapy ([Section 5.2](#)) by cycle day 42 (within 14 days of planned start of the subsequent cycle) will be considered dose limiting toxicity.
- Failure to receive at least 75% of the planned number of BAY 1895344 (elimusertib) doses during any cycle (i.e., 9 of 12 planned doses) due to delays attributable to myelosuppression would be considered a hematologic DLT.

5.5.2.1 Note: Grade 3 or 4 febrile neutropenia will not be considered a dose-limiting toxicity.

5.6: THERAPY DELIVERY MAPS (TDMS) FOR CYCLE 1

Page 1 of 1

Therapy Delivery Map – Cycle 1

This Therapy Delivery Map (TDM) relates to Cycle 1. Cycle 1 lasts 28 days. Please record the dose level in the chart below. Treatment may continue in the absence of unacceptable toxicity. Use a copy of this page once for Cycle 1.

This form is to be completed and uploaded into RAVE at the end of every cycle.

Criteria to start this cycle are listed in [Section 5.2](#). Extensive details are in [Section 5.0](#) and [Section 9.0](#).

This TDM is on 2 pages.

DRUG	ROUTE	DOSAGE	DAYS	IMPORTANT NOTES
BAY 1895344 (elimusertib) IND# [REDACTED]	Oral (Tablet)	_____ mg/m ² /dose BID Dose level 1 max dose = 40 mg BID Dose level -1 max dose = 30 mg BID Part B patients \geq 18 years old: 40 mg BID	1-3 8-10 15-17 22-24	On days that BAY 1895344 (elimusertib) is due to be given, it should be administered twice daily preferably at the same time of day each day. Take BAY 1895344 (elimusertib) one (1) hour before or two (2) hours after a meal with plenty of water.

Assigned Dose Level Ht cm Wt kg BSA m² Age \geq 18 years yes. no

Date Due	Date Given	Day	BAY 1895344 (elimusertib) Nomogram Dose mg qAM. _____ mg qPM	Studies
Enter actual dose administered below				
		PRE	_____ mg _____ mg	a-e, f*, g-i, j^, k, m#, n%, q\$, r@
		1	_____ mg _____ mg	a, b, d, e, f*, g, h, l, o&, p!
		2	_____ mg _____ mg	
		3	_____ mg _____ mg	o&
		4		
		5		
		6		
		7		
		8	_____ mg _____ mg	e, f* 1
		9	_____ mg _____ mg	
		10	_____ mg _____ mg	o&, p!
		11		
		12		
		13		
		14		
		15	_____ mg _____ mg	e, f*, 1
		16	_____ mg _____ mg	
		17	_____ mg _____ mg	
		18		
		19		
		20		
		21		
		22	_____ mg _____ mg	e, f*, j^, 1
		23	_____ mg _____ mg	
		24	_____ mg _____ mg	
		25		
		26		
		27		
		28		

* Please refer to [Section 8.1](#) for the specific timing of these observations.

Observations in Cycle 1

- a. History
- b. Physical Exam
- c. Performance Status
- d. Height, Weight, BSA
- e. Vital Signs
- f. CBC, differential, platelets: *Once weekly. If patients develop Grade 4 neutropenia or Grade 3 or 4 thrombocytopenia, CBC/differential/platelets should be checked at least twice per week (every 3-4 days) until recovery to Grade 3 neutropenia or Grade 2 thrombocytopenia, or until the criteria for dose limiting toxicity are met. For patients who experience hematological dose limiting toxicity, CBCs should be checked at least weekly until recovery of ANC and platelet count to eligibility criteria
- g. SGPT (ALT), Albumin, Bilirubin
- h. Electrolytes including serum creatinine, calcium (Ca⁺⁺), phosphorus (PO₄), magnesium (Mg⁺⁺)
- i. Creatinine Clearance or GFR
- j. Tumor disease evaluation: ^can occur any time during the last week of cycle 1. Should be obtained on the next consecutive cycle after initial documentation of either a PR or CR. Subsequent scans may restart 2 cycles after the confirmatory scan. Please note that for solid tumor patients, if the institutional investigator determines that the patient has progressed based on clinical or laboratory evidence, he/she may opt not to confirm this finding radiographically.
- k. Pregnancy test: Women of childbearing potential require a negative pregnancy test prior to starting treatment; sexually active patients must use an acceptable method of birth control. Abstinence is an acceptable methods of birth control. All women of childbearing potential must have a pregnancy test done every cycle prior to initiation of a new cycle.
- l. Medication Diary
- m. Pathology & Genomics Report: #Indicate a qualifying molecular aberration to enroll on study. Must be submitted via upload to MediData/RAVE. Details of genomic studies noted in [Section 4.1.4.3](#).
- n. Knee X-Ray: % Knee X-Ray should only be obtained in patients without epiphyseal closure at the time of enrollment, prior to start of therapy. If the baseline tibial radiographs demonstrate open growth plates (epiphysis) then knee X-rays for tibial growth plate assessment will be obtained after cycle 1, every 3 cycles thereafter and at the end of study treatment. The end of study treatment observation is not required, if already obtained within the final month of therapy. Reference [Section 8.7](#) for further instruction on monitoring for growth plate toxicity.
- o. Pharmacokinetics (required): &See [Section 8.5.2](#) for timing of PK studies
- p. Pharmacokinetics (optional): 'See [Section 8.3.5](#) for timing of optional PK studies
- q. Correlative Studies (required): \$See [Section 8.6](#) for details
- r. Correlative Studies (optional): @See [Section 8.3](#) for details

5.7: THERAPY DELIVERY MAPS (TDMS) FOR CYCLES 2 +

Page 1 or 2

Therapy Delivery Map – Cycle 2 +

This Therapy Delivery Map (TDM) relates to Cycle 2+. This TDM can be used for any dose level of BAY 1895344 (elimusertib). Please record the dose level in the chart below. Treatment may continue in the absence of unacceptable toxicity. Use a copy of this page once for Cycle 2 +.

This form is to be completed and uploaded into RAVE at the end of every cycle.

Criteria to start this cycle are listed in [Section 5.2](#). Extensive details are in [Section 5.0](#) and [Section 9.0](#).

This TDM is on 2 pages.

DRUG	ROUTE	DOSAGE	DAYS	IMPORTANT NOTES
BAY 1895344 (elimusertib) IND# [REDACTED]	Oral (Tablet)	mg/m ² /dose BID Dose level 1 max dose = 40 mg BID Dose level -1 max dose = 30 mg BID Part B patients ≥ 18 years old: 40 mg BID	1-3 8-10 15-17 22-24	On days that BAY 1895344 (elimusertib) is due to be given, it should be administered twice daily, preferably at the same time of day each day. Take BAY 1895344 (elimusertib) one (1) hour before or two (2) hours after a meal with plenty of water.

Assigned Dose Level Ht cm Wt kg BSA m² Age ≥ 18 years yes no

Date Due	Date Given	Day	BAY 1895344 (elimusertib) Nomogram Dose mg qAM. mg qPM	Studies
Enter actual dose administered below				
		1	mg mg	a-d, e*, f, g, i, j&
		2	mg mg	
		3	mg mg	
		4		
		5		
		6		
		7		
		8	mg mg	
		9	mg mg	
		10	mg mg	
		11		
		12		
		13		
		14		
		15	mg mg	e*
		16	mg mg	
		17	mg mg	
		18		
		19		
		20		
		21		
		22	mg mg	
		23	mg mg	
		24	mg mg	a-d, h^, j&, k!, l#
		25		
		26		
		27		
		28		

* Please refer to [Section 8.1](#) for the specific timing of these observations.

Cycle 2 +

Required Observations in Cycle 2 +

Page 2 or 2

- a. History
- b. Physical Exam
- c. Height, Weight, BSA
- d. Vital Signs
- e. CBC, differential, platelets: * **Must be obtained within 72 hours of the start of each cycle and on day 15 of all subsequent cycles.** If patients develops Grade 4 neutropenia or Grade 3 or 4 thrombocytopenia, CBC/differential/platelets should be checked at least twice weekly (every 3-4 days) until recovery to Grade 3 neutropenia, Grade 2 thrombocytopenia or until the criteria for dose limiting toxicity are met. For patients who experience hematological dose limiting toxicity, CBCs should be checked at least weekly until recovery of ANC and platelet count to eligibility criteria. Patients who have dose adjustment due to hematologic toxicity attributable to BAY 1895344 (elimusertib), are required to have CBCs once weekly to confirm the safety of this adjusted dose during the cycle. Please see [Section 6.1](#) for details.
- f. SGPT (ALT), Albumin, Bilirubin
- g. Electrolytes including serum creatinine, calcium (Ca⁺⁺), phosphorus (PO₄), magnesium (Mg⁺⁺)
- h. Tumor disease evaluation: ^**Can occur any time during the last week of cycles 2, 4 and 6 and then every 3 cycles thereafter.** Should be obtained on the next consecutive cycle after initial documentation of either a PR or CR. Subsequent scans may restart 2 cycles after the confirmatory scan. Please note that for solid tumor patients, if the institutional investigator determines that the patient has progressed based on clinical or laboratory evidence, he/she may opt not to confirm this finding radiographically.
- i. Medication Diary
- j. Knee X-Ray: & **Knee X-Ray should only be obtained in patients without epiphyseal closure at the time of enrollment, prior to start of therapy. If the baseline tibial radiographs demonstrate open growth plates (epiphysis) then knee X-rays for tibial growth plate assessment will be obtained after cycle 1, every 3 cycles thereafter and at the end of study treatment. The end of study treatment observation is not required, if already obtained within the final month of therapy.**
- k. Tumor Tissue for Immunohistochemistry pH2AX, pKAP1 and pATR (Optional): 'See [Section 8.3.3](#) for details.
- l. Tumor Tissue for Whole Genome Sequencing (Optional): #See [Section 8.3.1](#) for details.

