- ⁶ Must be obtained within 72 hours of the start of each cycle and on day 15 of all subsequent cycles. If patients develop Grade 4 neutropenia or Grade 3 or 4 thrombocytopenia, CBC/differential/platelets should be checked at least twice weekly (every 3-4 days) until recovery to Grade 3 neutropenia, Grade 2 thrombocytopenia or until the criteria for dose limiting toxicity are met. For patients who experience hematological dose limiting toxicity, CBCs should be checked at least weekly until recovery of ANC and platelet count to eligibility criteria. Patients who have a dose adjustment due to hematologic toxicity attributable to BAY 1895344 (elimusertib), are required to have CBCs checked once weekly to confirm the safety of this adjusted dose during the cycle. Please see [Section 6.1](#) for details.
- ⁷ If greater than 7 days from pre study labs, please collect CBC, differential, platelets, bilirubin, albumin and serum creatinine within 48 hours prior to cycle 1, dose 1. These labs must still meet eligibility to receive dose 1 (as per [Section 4.0](#)).

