11.2 Definitions

11.2.1 Evaluable for Adverse Events:

Any patient who receives at least one dose of BAY 1895344 (elimusertib) or who experiences a dose-limiting toxicity is considered evaluable for Adverse Events. In addition, during Cycle 1, patients not experiencing a DLT must receive at least 75% of the prescribed dose per protocol guidelines and must have the appropriate toxicity monitoring studies performed to be considered evaluable for dose limiting toxicity. Patients who do not have DLT and are not considered evaluable for dose limiting toxicity in Part A will be replaced.

11.2.2 Maximum Tolerated Dose:

- The MTD will be the maximum dose at which fewer than one-third of patients experience DLT (See [Section 5.5](#)) during Cycle 1 of therapy.
- In the unlikely event that two DLTs observed out of 6 evaluable patients are different classes of Adverse Effects (eg, hepatotoxicity and myelosuppression), AND all of the following conditions are met, expansion of the cohort to 12 patients will be considered:
 - One of the DLTs does not appear to be dose-related
 - The Adverse Effects are readily reversible
 - The study chair, PEP-CTN statistician, PEP-CTN committee chair or vice chair, and IND sponsor all agree that expansion of the cohort is acceptable

If fewer than 1/3 of patients in the expanded cohort experience dose-limiting toxicities, the dose escalation can proceed.

- The DLTs observed in the pharmacokinetic (PK) expansion cohort will contribute towards the total number of DLTs observed at the RP2D/MTD during the dose escalation portion of the

study. If $\geq 1/3$ of the cohort of patients at the RP2D/MTD (during the dose escalation plus the PK expansion) experience DLT then the MTD will be exceeded.

- If required number of responses per the Simon two-stage design for expansion is not met for either the ARMS or EWS phase 2 cohorts whilst the PK expansion is still enrolling, the PK expansion will subsequently be closed to those patients.

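### Cycle 1 schedules no liver or electrolyte chemistry between Day 1 and the pre-Cycle 2 draw, so transient laboratory DLTs can be missed in the window that sets the RP2D

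*Combined protocol and SAP*

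**What the plan says.** Section 5.5 fixes the window: "The DLT observation period for the purposes of study dose-escalation (Part A) will be the first cycle of therapy". Section 5.5.1.1 makes a DLT of "Any Grade 3 or greater non-hematological toxicity attributable to protocol therapy with the specific exclusion of" a short list. Two items on that list depend on later laboratory values. One is "Grade 3 liver enzyme elevation, including ALT/AST/GGT that returns to Grade" 1 or lower within 7 days; the other is "Grade 3 hypophosphatemia, hypokalemia, hypocalcemia or hypomagnesemia responsive to supplementation".

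The Cycle 1 delivery map (5.6) defines the chemistry as observation "g. SGPT (ALT), Albumin, Bilirubin" and observation h, "Electrolytes including serum creatinine, calcium", phosphorus and magnesium. Both appear in the pre-treatment row and the Day 1 row only. Days 8, 15 and 22 carry vital signs, CBC and diary, with the tumor evaluation added on Day 22. In its Cycle 1 column, Section 8.1 marks the CBC as weekly and gives each chemistry row a plain X. The change log says these observations were placed on Day 1 of Cycle 1 to agree with Section 8.1, so Day 1 appears intended.

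The next chemistry belongs to Cycle 2 and may be drawn up to 72 hours before that cycle. At the end of study treatment, chemistry is done only if clinically indicated. The CBC has a twice-weekly repeat rule after severe cytopenia; chemistry has no repeat rule. AST and GGT are graded in Appendix IV but are in no scheduled panel.

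Under Section 11.2.1 a patient without a DLT "must have the appropriate toxicity monitoring studies performed to be considered evaluable for dose limiting toxicity". No chemistry frequency is given there, and Sections 11.8 and 12.2.1.1 do not repeat the condition.

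**The concern.** Part of the DLT definition rests on laboratory values that the schedule does not collect during most of the DLT window. A site can follow the plan exactly and record a patient as evaluable without a DLT when no chemistry was drawn after Day 1. This error runs one way, because an event that is not looked for can only be left out of the count.

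The count matters at small numbers. Under Section 11.3, two DLTs among up to six patients mean the MTD has been exceeded. Under Section 5.3.2, the dose chosen in Part A then applies to every Part B patient under 18. The toxicity description in primary aim 1.1.4 uses the same data.

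**Working it through.** The plan gives no figure on this point, so there is none to reproduce. The check has three steps; the last two are illustrations on stated assumptions.

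**1. The gap.** Scheduled chemistry falls before treatment, on Day 1, and then at the pre-Cycle 2 draw. With a 28-day cycle, Day 1 of Cycle 2 is Day 29, and 72 hours earlier is Day 26. The gap after Day 1 is therefore 25 to 28 days and spans all four dosing blocks (Days 1-3, 8-10, 15-17, 22-24).

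**2. Share of episodes met by a scheduled draw.** Assume a Grade 3 episode starts with equal chance on any of Days 2-24 (23 days), lasts L days, and the pre-Cycle 2 draw is on Day 27. An episode starting on day o covers days o to o + L - 1, so it is met if 28 - L ≤ o ≤ 24.

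| L (days) | Onsets met | Share, current schedule | Share with Days 8, 15, 22 added |
|---|---|---|---|
| 7 | 21-24 | 4/23 = 17% | 100% |
| 10 | 18-24 | 7/23 = 30% | 100% |
| 14 | 14-24 | 11/23 = 48% | 100% |
| 21 | 7-24 | 18/23 = 78% | 100% |

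Moving the draw one day either way changes each current-schedule count by one onset in 23, about 4 percentage points. For a patient who leaves at the Cycle 1 scan and has no unscheduled test, every entry in the current-schedule column becomes 0%.

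A second set of assumptions (onset uniform over the 28 days from Day 1 to Day 29, one end-of-cycle draw) gives L/28: 25% at 7 days, 50% at 14 and 75% at 21. Adding weekly draws gives 96% to 100% from 7 days up. The 7-day row is the boundary case for liver enzymes, since an enzyme rise that resolves sooner is excluded anyway.

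**3. Effect on the dose decision.** Let p be the true DLT rate and s the share of DLTs that show only in chemistry. Assume a quarter of those are caught, the 7-day result under the second set. The observed rate is p × (1 - 0.75s). Treat the rule as a fixed six patients, a simplification of the rolling six. The chance of 0 or 1 observed DLT is (1 - q)^6 + 6q(1 - q)^5, where q is the observed rate.

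For p = 0.33:
- s = 0: q = 0.330, chance 36%
- s = 10%: q = 0.305, chance 41%
- s = 25%: q = 0.268, chance 49%
- s = 50%: q = 0.206, chance 64%

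The documents do not give s, so this is a range and not an estimate.

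**The case against.** A reader might infer that laboratory DLTs cannot be seen at all in Cycle 1. The documents do not support that. The pre-Cycle 2 draw may fall on Days 26-28, inside the window, and Section 5.2 requires it to meet eligibility. The ALT limit for eligibility (135 U/L) equals the top of Grade 1 in Appendix IV, so an ALT rise that persists to that draw would be found before Cycle 2. Unscheduled tests are allowed. This answer is partial: the draw depends on Cycle 2 starting, eligibility sets no electrolyte limit, and one value shows neither onset nor duration.

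A reader might also infer that the untimed 7-day clause lowers the count. It does the reverse. Grade 3 is a DLT by default and recovery within 7 days is the exception. A detected rise without a timely repeat stays a DLT, so only non-detection biases the count downward.

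Nor are patients unmonitored. Vital signs, CBC and diary are weekly in Cycle 1. Section 6.2 ties continued treatment after a non-hematological DLT to recovery, Section 13.5.4 defines a resolution date for adverse events, and Section 10.1 keeps patients who stop during Cycle 1 on the Section 8.1 observations. These provisions follow up events already found or repeat the Section 8.1 schedule; none adds a chemistry draw.

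It is tempting to say later cycles are watched more closely, because Section 8.1 footnote 6, attached to the Cycle 2+ chemistry cells, begins "Must be obtained within 72 hours of the start of each cycle and on day 15 of all subsequent cycles". But the rest of that footnote concerns CBCs, and the Cycle 2+ map attaches the same text to the CBC and lists only the CBC on Day 15. The comparison is unsafe.

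The strongest objection is about size. In the adult escalation table (2.3.2) the DLTs are cytopenias plus one Grade 2 fatigue. The agent's risk list (9.1.9, 197 patients) places ALT and AST increases, hypokalemia and hypophosphatemia among events with insufficient evidence of causation. That favors the low end of the range in step 3, though adult data do not rule out such events in children.

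**Conclusion.** The point stands as a gap in ascertainment. No chemistry is scheduled for 25 to 28 days of the DLT window, and many transient Grade 3 laboratory events would not be met by a scheduled draw: 17% to 78% are met for durations of 7 to 21 days, on the assumed onset and a Day 27 draw. The figure is zero for a patient who leaves at the Cycle 1 scan without unscheduled tests. Undetected events bias the DLT count downward; detected enzyme rises that cannot be timed default to DLT. AST and GGT are in the rule but never scheduled.

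The effect on the dose decision is unknown. It depends on the laboratory-only share of DLTs, and the adult experience suggests that share is small. This should be fixed because the fix is cheap and concerns the primary endpoint of Part A. The documents do not show that the dose decision would be wrong.

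**What to change.** Reconcile Section 5.5.1.1, the Cycle 1 map (5.6), the Cycle 1 column of Section 8.1 and the evaluability rule in 11.2.1 as follows:

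- Collect observations g and h for DLT ascertainment at the weekly Cycle 1 visits (Days 8, 15, 22) that already carry the CBC.
- After a Grade 3 value, require repeat values sufficient to apply the 7-day clause.
- State in 11.2.1 which chemistry a patient must have to count as evaluable without a DLT, and align 11.8 and 12.2.1.1.
- Either add AST and GGT to the panel or remove them from the clause.
- State whether Day 15 in Section 8.1 footnote 6 applies to chemistry or only to the CBC, and make the Cycle 2+ map agree.

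The cost is a schedule amendment and about three small chemistry panels per patient at existing visits, plus repeats after Grade 3 values. For the anticipated Part A maximum of 23 patients that is 3 × 23 = 69 panels; if applied to all 90 planned patients, 3 × 90 = 270. No extra patients are needed, and no extra scheduled visits apart from any needed for repeats.

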5.2 Criteria for Starting Subsequent Cycles

A cycle may be repeated every 28 days if the patient 1) has at least stable disease 2) all pre-cycle studies required per [Section 8.1](#) meet eligibility criteria-as defined in [Section 4.0](#) and 3) is otherwise eligible to continue agent administration per the requirements in [Section 6.0](#).

5.2.1 Recommendations for Starting Each Weekly 3-day Course:

BAY 1895344 (elimusertib) is administered on a 3-day on and 4-day off schedule, repeated 4 times each cycle. Hematologic toxicities are the most common toxicities with BAY 1895344 (elimusertib). Eligibility criteria require an ANC \geq 1000/ μ L and Platelets \geq 100,000/ μ L, hence these parameters also need to be met to start any cycle (See [section 4.1.11.1](#)). Once a cycle has started, patients are required to have an ANC $>$ 500/ μ L and Platelets $>$ 50,000/ μ L within 48 hours prior to initiation of each 3 day interval of BAY 1895344 (elimusertib) administration (i.e. ANC and platelet parameters must be met (without transfusion) within 48 hours of initiation of days 8, 15, and 21). If parameters are not met, this 3-day interval of BAY 1895344 (elimusertib) will be omitted and attempted to restart the following week (e.g. day 15 or 21). If more than one 3-day block of BAY 1895344 (elimusertib) is missed within a cycle (i.e. $<$ 75% of planned therapy is given for a particular cycle), that would be considered a hematologic DLT.

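### The 75% dose-delivery DLT rule counts dosing days as doses (9 of 12 should be 18 of 24); secondarily, the day-42 count-recovery DLT should be tied explicitly to Cycle 1

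*Combined protocol and SAP*

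**What the plan says.** **Dose delivery.** Section 5.5.2 counts it as a hematologic DLT when myelosuppression keeps a patient below 75% of the planned doses in any cycle, and puts that threshold at 9 of 12 doses. Section 5.1 and the Cycle 1 therapy delivery map (5.6) schedule the drug twice daily on days 1-3, 8-10, 15-17 and 22-24. Section 5.2.1 states the same 75% limit in blocks: missing more than one of the four 3-day blocks is a DLT.

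**DLT window.** Section 5.5: "The DLT observation period for the purposes of study dose-escalation (Part A) will be the first cycle of therapy". The Cycle 1 map: "Cycle 1 lasts 28 days". Section 11.2.2: "The MTD will be the maximum dose at which fewer than one-third of patients experience DLT", limited in the same sentence to Cycle 1. Section 5.5.2 nevertheless lists a count-recovery DLT: failure to meet the criteria for weekly dosing or the next cycle "by cycle day 42 (within 14 days of planned start of the subsequent cycle) will be considered dose limiting toxicity". The cycle-start counts are ANC at least 1000/µL and platelets at least 100,000/µL; 5.2.1 says of them, "hence these parameters also need to be met to start any cycle". Weekly dosing within a cycle needs only ANC above 500 and platelets above 50,000.

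**The concern.** The dose count stands inside the definition that drives the Part A dose decision. Someone scoring DLTs from a diary of individual doses could apply a floor of nine doses, half the correct number.

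The window raises a different question. A failure that can be declared as late as day 42 does not fit a period of 28 days read strictly. Section 11.3 holds patients who cannot yet be assessed as pending, but names no day. A patient below cycle-start counts at day 28 could therefore be scored as without DLT, held as pending, or later counted as a DLT, and the plan does not say which. Myelosuppression was the main dose-limiting toxicity in adults (2.3.2), and the Part A dose is given to every Part B patient under 18 (5.3.2), so the scoring should not depend on the reader.

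**Working it through.** **Dose count.** Inputs: twice daily (5.1); 3-day blocks, 4 per cycle (5.1, 5.2.1); threshold 75% (5.5.2).

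- The plan's figure: 3 × 4 = 12 and 0.75 × 12 = 9. This reproduces 9 of 12, but in dosing days.
- In doses: 2 × 3 × 4 = 24 and 0.75 × 24 = 18. Nine doses would be 9/24 = 37.5%.

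| Blocks missed | Doses taken | Share | DLT with floor of 18 | DLT with floor of 9 | DLT under 5.2.1 |
|---|---|---|---|---|---|
| 0 | 24 | 100% | no | no | no |
| 1 | 18 | 75% | no | no | no |
| 2 | 12 | 50% | yes | no | yes |
| 3 | 6 | 25% | yes | yes | yes |

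The two floors disagree for totals of 9 to 17 doses. The only whole-block total in that range is 12, and 5.2.1 already makes it a DLT. A part-block total in the range, such as 16 (16/24 = 66.7%), is settled by the 75% in the same 5.5.2 sentence.

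**Window.** 28 + 14 = 42, so the plan's day reproduces. The last scheduled dose is on day 24, and 42 − 24 = 18 days later.

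The patient in question has ANC of at least 500 but below 1000, or platelets of at least 50,000 but below 100,000, at day 28. For example, platelets of 80,000 after all 24 doses pass the weekly criterion, meet no other 5.5.2 criterion, and do not permit Cycle 2.

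The 11.3 table has six states that accept the dose (DLT / without DLT / pending). The table below shows the decision if one patient without DLT is held as pending, or becomes a late DLT:

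| Accepted state | One held pending | One becomes a late DLT |
|---|---|---|
| 0/3/0 | same dose level | same dose level |
| 0/4/0 | same dose level | same dose level |
| 0/5/0 | same dose level | same dose level |
| 0/6/0 | accepted | accepted |
| 0/5/1 | suspend | suspend |
| 1/5/0 | suspend | de-escalate |

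Only 1/5/0 goes from acceptance to de-escalation: 1/6 = 16.7% becomes 2/6 = 33.3%. Even then, if the two DLTs are of different classes and the other 11.2.2 conditions hold, "expansion of the cohort to 12 patients will be considered". Acceptance would then need at most 3/12 = 25%, since 4/12 = 33.3% is not below one-third. If the first DLT was also myelosuppression, that route is closed.

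**The case against.** **Attribution.** A reader might infer that the plan contradicts itself, or that it excludes late count failures from the MTD tally. The documents do not support that. Numbering the deadline as day 42 of the cycle counts from the start of the cycle just given, and 6.1.3 counts its 42 days in the same way. The pending category in 11.3 is defined by status, not by calendar day, so it can hold such a patient. This largely stands: scoring to Cycle 1 is the more natural reading. What remains is that 5.5.2 also governs dose reduction in later cycles, so being listed there does not by itself place an event in the Part A tally.

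**Monitoring.** A reader might infer that counts go unobserved after day 28. They do not. Section 10.1 requires ongoing adverse events, and those emerging within 30 days of the last dose, to be followed; from day 24 that reaches day 54. A patient who continues needs a qualifying CBC within 72 hours of starting Cycle 2 (8.1). The residue is small. No CBC interval is set for moderately low counts, because the twice-weekly rule starts only at Grade 4 neutropenia or Grade 3-4 thrombocytopenia. Resolution in 13.5.4 means baseline or Grade 1 or lower, not the cycle-start counts.

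**Effect.** A reader might infer from the 11.3 table that five of the six acceptance decisions are fragile. Four of those five changes are continued accrual at the same dose or a suspension, and 0/3/0 lies below the minimum of 4 DLT-evaluable patients in 11.1. Suspected DLTs are reported within 24 hours (5.4), evaluations are reviewed weekly (14.5.2), and PK-expansion DLTs are pooled at the RP2D (11.2.2). These bound the consequences but do not state the rule.

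**Dose count.** It is a unit slip beside a correct percentage. That is fair as to its effect, but not a reason to leave it in a DLT definition.

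**Conclusion.** The dose count is wrong as written: 75% of a cycle is 18 of 24 doses. This rests only on the schedule. A reader might infer that the plan operates a 37.5% threshold. It does not, since 5.5.2 itself says 75% and 5.2.1 gives the right rule in blocks, so few if any patients would be reclassified.

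The day-42 item is a secondary, low-cost alignment. The likely intent can be read from the text, but 5.5, 11.2.2 and 11.3 do not state it. Its demonstrated reach is one acceptance state that would move to de-escalation, among patients evaluable for hematologic toxicity (at least 5 of every 6 under 4.1.11.1). No probability can be attached, because the documents give no rate of late count failure. With 18 days between the last scheduled dose and day 42, few patients may be affected.

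**What to change.** In 5.5.2, replace the parenthetical count with: 18 of 24 planned doses (9 of 12 dosing days). This costs nothing.

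In 5.5, 11.2.2 and 11.3, state that a Part A patient below cycle-start counts at day 28 stays pending until Cycle 2 starts or day 42, whichever comes first; that a count failure in that window is a Cycle 1 DLT; and that CBCs are weekly during it. The cost is a wording amendment, up to 14 more days before some dose decisions, and about two CBCs (14/7 = 2) for each affected patient.

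Do not add a rule that missing counts on days 29-42 make a patient non-evaluable. Section 11.2.1 already asks for 75% of the Cycle 1 dose and says patients without DLT "must have the appropriate toxicity monitoring studies performed to be considered evaluable for dose limiting toxicity"; it then provides that "Patients who do not have DLT and are not considered evaluable for dose limiting toxicity in Part A will be replaced". Extending that to the later window could discard a child who completed Cycle 1 and stopped for progression, and expose another child to replace them.
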